- (1) Adult men and woman with a diagnosis of PD.
- (2) Patients who are candidates for bilateral STN DBS placement surgery and who will receive this treatment as part of their routine care.
- (3) Willingness to undergo temporary changes in STN DBS generator settings.

PROTOCOL TITLE: Safety and feasibility of using low frequency deep brain stimulation of the subthalamic nucleus to improve cognitive performance in patients with Parkinson's disease

(4) Patients who have a caregiver who is willing to answer psychological screening questions on behalf of the patient.

Exclusion criteria:

- (1) Patients less than 18 years of age.
- (2) Patients who are not candidates for bilateral STN DBS placement surgery.
- (3) Adults unable to consent
- (4) Pregnant woman
- (5) Prisoners
- (6) Patients who score over 20 on the BDI indicating moderate depression

7) Number of Subjects

The target sample size is 22 subjects. The study design is a phase 1 safety and feasibility study. While results may show a trend towards efficacy, we will not be able to power the study toward efficacy. Two of these subjects will be used to evaluate the ease of use of the computerized cognitive test, but will not participate in any other study procedures and data will not become part of the study record. All subjects are to be enrolled locally at UC Davis medical center.

8) Recruitment Methods

a) Study-Wide:

NA

b) Local:

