a) Neuropsychiatric tests. We will perform the BDI and NPI at baseline, at the first experimental session, once by telephone call after 24 hours of LFS, and a fourth time at the final experimental session. The score of the BDI will be compared across sessions and a score that rises above 20 will be considered positive for the development of moderate depression. The NPI assesses frequency, change in severity, and caregiver distress over 12 neuropsychiatric domains and we will look for caregiver reports of significant change across these domains.

b) Motor tests. The Unified Parkinson's Disease Rating Scale (UPDRS) will be performed prior to patient's surgery as part of the patient's routine care. We will repeat the scale at the final experimental session to assess changes in motor symptoms after sustained LFS.

c) Changes in cognitive function will also be assessed as described below.

2. Feasibility. Improvement in cognitive function will be measured by three cognitive tests: the Stroop test, the N-Back test, and the verbal fluency test. We will measure reaction time and error rates and look for significant changes across stimulator frequencies. The results from 20 patients will help us determine if a large-scale study of effectiveness is warranted and feasible.

Describe any primary or secondary safety endpoints.

See above.

PROTOCOL TITLE: Safety and feasibility of using low frequency deep brain stimulation of the subthalamic nucleus to improve cognitive performance in patients with Parkinson's disease

12) Procedures Involved

a) Describe and explain the study design.

The study design is a safety and feasibility study. We aim to identify 20 PD patients who will receive bilateral STN DBS as part of their standard care. We plan to measure the safety of LFS in the STN as measured through psychological, cognitive, and motor scales, and compare cognitive performance with low and high frequency STN DBS. We propose that LFS in the theta range will not negatively affect psychiatric symptoms or alter motor symptoms, and will improve performance on tests of executive functioning.

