without stimulation and will complete the BDI. Informers will complete the NPI. Subsequently, the stimulators will be turned on, and each patient will repeat cognitive testing under gamma frequency (~130 Hz) and theta frequency stimulation (~5 Hz). The order of stimulation will be randomized. Stimulation will occur for 5 minutes prior to and continuously throughout each task. Amplitude and pulse width will be set to 3 V and 120 microseconds accordingly (Laxton & Lozano 2013) or as tolerated by the patient, and will remain constant across sessions. We will wait 20 minutes between testing conditions to elicit about 75% of DBS effects (Temperli et al 2003). At the end of the experimental testing session, the stimulator will be turned off or set to LFS in preparation for the second experimental session.

The second on-site experimental testing session will assess the effects of continuous theta stimulation on cognitive function. Patients will repeat cognitive testing after 48 hours of continuous theta stimulation. This second on-site testing session will occur 3-5 days following the first experimental session. Two days prior to the testing session, patients' stimulators will be turned on to the theta frequency stimulation setting and patients will return home and engage in normal activities. After 48 hours they will return to the clinic and repeat cognitive testing with continuous theta frequency stimulation. The UPDRS, NPI, and BDI will also be performed at this time. At the end of the session, their stimulators will be turned off.

We will screen for psychological changes by telephone once during the 2 day stimulation period. The patient will complete the BDI and a relative or caregiver will complete the NPI over the phone.

The structure of the experimental sessions is shown in Figure 2 and Figure 3.

[figure not shown]

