Figure 2: Stimulation schedule. The first experimental session (E1) will include 30 minutes of baseline cognitive testing. Stimulation will then be turned on (Stim) for 5 minutes prior to cognitive testing under the first frequency condition (either HFS or LFS depending on randomization) (Cog C1). Stimulation will then be turned off and the patient will have a 15 minute rest period. Stimulation at the second testing frequency condition will then be turned on for 5 minutes and the cognitive testing will be repeated (Cog C2). At the completion of this session, LFS will be turned on for 48 hours. When the patient returns to clinic for the second experimental session (E2) they will repeat cognitive testing after sustained LFS (Cog S-Stim). The stimulation will be turned off and the patients will return home to continue standard care. Shaded boxes represent periods of stimulation.

PROTOCOL TITLE: Safety and feasibility of using low frequency deep brain stimulation of the subthalamic nucleus to improve cognitive performance in patients with Parkinson's disease

[figure not shown]

Figure 3: Safety Measures. Motor, psychological and cognitive tests present for each patient contact are indicated. *This motor test performed by neurologist as part of routine care and occurs at a clinic visit prior to the patient’s anticipated surgery.

We will also identify and enroll two subjects that have PD in order to test the ease of use of the computerized cognitive test, prior to the enrollment of additional subjects. These subjects will perform the computerized cognitive test once and will not participate in any other study procedures. We will use this information to decide on optimal parameters within the computerized cognitive test such as stimulus presentation time and response time allowed.

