We will also examine changes in psychological symptoms. For each individual patient, we will measure the BDI and NPI at baseline, at the first experimental session, by phone call after 24 h LFS, and at the final experimental session. For the BDI, we will consider any score greater or equal to 20 as evidence of moderate depression and will terminate the study for any individual that shows evidence of depression. At the group level, we will calculate

PROTOCOL TITLE: Safety and feasibility of using low frequency deep brain stimulation of the subthalamic nucleus to improve cognitive performance in patients with Parkinson's disease

the percentage of people that develop depression. For the NPI, we will calculate the total score. At the individual level we will look for the development of new symptoms in the 12 subsections. At the group level we will perform an ANOVA to look for significant changes across the 3 time points.

Cognitive Data Analysis:

The cognitive data analysis will examine the effect of theta frequency stimulation on cognitive task performance. Analyses for the Stroop task will include the examination of response time and error rates across stimulator settings. Two (trial type: congruent vs incongruent) by three (Setting: low, high, no stimulation) ANOVAs will be performed for both reaction time and accuracy. Post conflict and post error reaction time adjustments will also be examined across stimulator settings. For the N-back test, ANOVAs will also be performed to assess the effects of complexity (1,2-back) and stimulation frequency (none, high, low) on error rates. For the verbal fluency test, the average number of words generated across stimulation conditions and the change in word number on low and high frequency stimulation settings will be compared. Analyses will be performed using MATLAB and STATA.

Describe any procedures that will be used for quality control of collected data.

a.) Study-Wide:

NA

b.) Local

Describe the local procedures for maintenance of confidentiality.

This research is partly funded by a donation from the Chevo Foundation. The Chevo Foundation will not have access to any of the study documents including the data.

Data files to be stored include group assignment, background information, any head scans if performed, and results from neurocognitive and motor tests.

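### The LFS/HFS order is randomised with no stated balance and analysed without a period term, so any net practice or fatigue effect costs precision on the LFS minus HFS contrast

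*Combined protocol and SAP*

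**What the plan says.** Section 12a describes E1 as testing without stimulation, followed by testing at about 130 Hz and about 5 Hz. On the sequence of the two frequencies it says "The order of stimulation will be randomized". The Figure 2 legend adds that the first stimulated condition (C1) is "either HFS or LFS depending on randomization", with the other frequency second (C2). No section states blocking, counterbalancing or a ratio of the two sequences.

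The analyses are in section 14, Cognitive Data Analysis. For Stroop: "Two (trial type: congruent vs incongruent) by three (Setting: low, high, no stimulation) ANOVAs will be performed for both reaction time and accuracy". For N-back: "ANOVAs will also be performed to assess the effects of complexity (1,2-back) and stimulation frequency (none, high, low) on error rates". For fluency, "the change in word number on low and high frequency stimulation settings will be compared". None mentions period or sequence.

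Section 7 sets the target at 22, of whom two only try out the computerised test, which leaves 20. It also says "we will not be able to power the study toward efficacy". Section 11 nevertheless gives the cognitive results a use: "The results from 20 patients will help us determine if a large-scale study of effectiveness is warranted and feasible".

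**The concern.** The stimulated part of E1 is a two-period, two-sequence crossover. The battery takes about 30 minutes per condition and is repeated after about 20 minutes, in patients about three weeks past lead surgery. Practice or fatigue between C1 and C2 is plausible, and randomising the order only makes sense if order might matter. The analysis then leaves that order out.

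Two things follow if the net period effect is not zero. An uneven split carries part of it into the observed LFS minus HFS difference. Also, with no period term, the standard error reported for that difference need not match its true spread. Aim 2 in section 4 rests partly on this contrast, and so does the decision on a larger study.

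**Working it through.** The documents give no effect size, SD, significance level or power, so there is no planned figure to reproduce. The 22 is a headcount (20 + 2).

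**Inputs.** n = 20 (sections 7 and 11). Two sequences (section 12a, Figure 2). Assumed: simple randomisation, no carry-over, two-sided 5% tests, and a period effect π (C2 minus C1) of 0 to 0.8 in units of the SD of the paired difference, so that SD = 1.

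**Model.** For patient i, the LFS minus HFS difference is d = τ + sπ + e, with s = +1 if LFS comes second and −1 if it comes first.

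**Chance of imbalance**, Binomial(20, 0.5):
- exactly 10:10: 0.176
- 12:8 or worse: 0.503
- 13:7 or worse: 0.263
- 14:6 or worse: 0.115

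**Shift given the split.** With k patients having LFS second, the estimate moves by π(2k − 20)/20. At k = 13 this is π × 6/20 = 0.3π. At k = 14 it is 0.4π. Its average over repeated randomisation is zero.

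**Spread and reported error without a period term**, as multiples of the standard error when π = 0:
- True spread, simple randomisation: √(1 + π²).
- Error reported by a paired test, simple randomisation: the same on average, because chance imbalance is already in the sample variance.
- Error reported by a paired test, 10:10 order: √(1 + π² × 20/19), since 4 × 10 × 10/(20 × 19) = 20/19. The true spread is then 1.
- Error reported from the pooled three-level ANOVA: about √(1 + π²/2). Order noise enters only one of the two within-patient contrasts, and pooling averages it with the other (sphericity assumed).

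| π | True spread, simple | Paired error, 10:10 order | Pooled ANOVA error |
|---|---|---|---|
| 0 | 1.00 | 1.00 | 1.00 |
| 0.2 | 1.02 | 1.02 | 1.01 |
| 0.3 | 1.04 | 1.05 | 1.02 |
| 0.5 | 1.12 | 1.12 | 1.06 |
| 0.8 | 1.28 | 1.29 | 1.15 |

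**Type I error by simulation.**
- Paired test, simple randomisation: about 0.05 throughout.
- Paired test, balanced order, no period term: about 0.041 at π = 0.3 and 0.030 at 0.5, so conservative.
- Pooled ANOVA error, simple randomisation: about 0.055, 0.062 and 0.076 at π = 0.3, 0.5 and 0.8, so too liberal.

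**Power by simulation**, paired test, true difference 0.66 SD. With simple randomisation and no period term it is about 0.80, 0.78, 0.77, 0.71 and 0.59 at π = 0, 0.2, 0.3, 0.5 and 0.8. With a 10:10 order and a period term it stays at about 0.80 throughout.

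**Price of the period term.** Residual degrees of freedom fall from 19 to 18, and the difference detectable with 80% power at π = 0 moves from 0.660 to 0.662 SD.

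**The case against.** The best reply is that the period effect may be small. Each patient has already done the battery before surgery and again without stimulation at the start of E1, so C1 and C2 are the third and fourth runs. Stroop keys are trained beforehand, there is a rest between conditions, and practice and fatigue pull in opposite directions. This stands. At 0.2 SD the loss is about 2%, and under an unblocked order a period term would then slightly lower power (0.775 against 0.784). It argues for balancing the order as well as adding the term, and for showing a range that includes zero.

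Section 14 looks for setting effects and, for Stroop, also crosses setting with trial type. A practice shift common to congruent and incongruent trials cancels from that interaction. This stands too; the point concerns the setting contrast.

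The study also disclaims efficacy power and sets no numerical threshold for going on. That limits how serious the point is. It is no reason to accept avoidable noise in 20 patients.

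A reader might infer more than the documents support:
- That precision is always lost. It is not when the net period effect is zero.
- That the LFS minus HFS estimate is biased. It is shifted only conditionally on the realised split.
- That the error bars are too wide. The direction depends on whether the order is balanced and on which error term is used, and section 14 does not say.
- That the trial is worth only 12 patients. That figure is 20/(1 + 0.8²) = 12.2 and rests wholly on the top of the assumed range.
- That randomisation is known to be simple. The protocol is silent, and a balanced list may have been intended.

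**Conclusion.** The point holds as a gap in design and analysis that is cheap to close. It does not invalidate the study. Two facts are firm: no balance of the LFS/HFS order is stated, and no planned analysis uses the order. The size is not firm. It depends on a period effect that the documents do not give, and runs from nothing at 0 to a 28% wider true spread at 0.8 SD. The 18% chance of an exact 10:10 split and the 26% chance of 13:7 or worse also require simple randomisation.

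Without a period term, the reported error is too wide if the order is balanced, about right for a paired test under simple randomisation, and too narrow if the pooled three-level error is used under simple randomisation.

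LFS versus no stimulation is a separate problem. No stimulation is always tested first in E1, so that comparison is confounded with period whatever is done about the LFS/HFS order.

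**What to change.** In section 12a, state that the LFS/HFS order is allocated 1:1 in blocks, for example two of each sequence within every four patients. This gives 10:10 over 20 patients and fits the safety reviews after 4, 8, 12 and 20.

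Name who holds the list, and make it someone who does not administer the cognitive tests. Section 24 needs attention here: all three roles it lists include administering cognitive tasks, and the principal investigator also reprograms the generator.

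In section 14, estimate LFS minus HFS within patient with a period term for Stroop, N-back and fluency, and show the results by sequence. Both parts are needed: balance alone leaves period variance in the reported error, and a period term alone loses some efficiency when the split is uneven. Withdrawals may disturb 10:10, and the period term then still removes the conditional shift.

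The cost is an allocation list, one degree of freedom (0.660 to 0.662 SD) and some predictability of the last allocations in each block. No visit, test or stimulation setting changes. Section 14 should also say that this analysis does not resolve LFS versus no stimulation.

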The protected health information will not be reused or disclosed to any other person or entity, except as required by law, for authorized oversight of the research study, or for other research for which the use of disclosure of PHI for which an authorization or opportunity to agree or object is not required by 45 CFR 164.512. The research could not be practicably conducted without the waiver, and without access and use of the PHI for recruitment.

9) Compensation to the Subjects

Subjects will be compensated \$10 per session. If the patient decides not to participate in further sessions, they will still receive the compensation for the completed sessions. Travel expenses up to \$30 per patient will be provided if needed. The compensation will be in the form of a gift card and will be given at the time of the visit.

PROTOCOL TITLE: Safety and feasibility of using low frequency deep brain stimulation of the subthalamic nucleus to improve cognitive performance in patients with Parkinson's disease

10) Study Timelines

The duration of the study from subject enrollment of the first patient to final data analysis will be approximately two years. Each individual subject will participate in the study for a maximum of 2 months for a total of 3 on-site experimental sessions and one telephone call. The first on-site visit will occur within the month prior to their planned DBS placement surgery, following the pre-operative visit. The second and third on-site visits will occur within the fourth week after the DBS electrode placement surgery, 3-4 days apart. A telephone call will be made 24 hours prior to the third on-site session to obtain additional safety information (Figure 1). Each participant will remain in the study for approximately 2 months from the time of consent. Participation is on a voluntary basis and subjects will reserve the right to withdraw participation in the study at any point of time. We expect the duration to enroll all study subjects will be approximately 2 years based on the number of patients who meet the inclusion and exclusion criteria.

We expect to complete the study by July 2017. The data will be analyzed as individual patients complete the study with further analyses after data collection is complete.

11) Study Endpoints

1. Safety: Safety endpoints will be measured by neuropsychiatric, motor, and cognitive testing:

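### The start of sustained LFS is stated two ways: counted from E1 it gives 72-120 h at E2 instead of 48 h; counted back from E2 it needs a switch-on missing from the visit count

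*Combined protocol and SAP*

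**What the plan says.** **Intended exposure.** Section 12: "Patients will repeat cognitive testing after 48 hours of continuous theta stimulation". Stimulation is to be still running during testing at E2 and is switched off when that session ends.

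**Start of LFS.**
- Figure 2 caption (section 12), on the end of E1: "At the completion of this session, LFS will be turned on for 48 hours".
- Section 12 text, on the end of E1: "the stimulator will be turned off or set to LFS in preparation for the second experimental session". No rule says which patients get which state.
- Section 12 text, on the period two days before E2: "stimulators will be turned on to the theta frequency stimulation setting and patients will return home and engage in normal activities".

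**Gap from E1 to E2.**
- Section 12: "This second on-site testing session will occur 3-5 days following the first experimental session".
- Section 10: "The second and third on-site visits will occur within the fourth week after the DBS electrode placement surgery, 3-4 days apart". The second and third on-site visits are E1 and E2.

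**Contacts.**
- Section 10 describes participation as "for a total of 3 on-site experimental sessions and one telephone call".
- It times the call from E2: "A telephone call will be made 24 hours prior to the third on-site session".
- Sections 11 and 14 time the same call from the start of LFS, at 24 h of exposure.

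**Calendar.** Section 12 places E1 on days 22-24 after lead surgery. It also says the study ends before treatment stimulation normally begins, typically 4 weeks after that surgery.

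**The concern.** The two start times agree only if E2 falls two days after E1, and neither stated gap allows that. Staff who follow the caption, or who use the option of leaving LFS on after E1, deliver a different exposure from staff who switch on two days before E2.

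This exposure underlies Aim 3 (section 4). E2 holds the only UPDRS after LFS and the only cognitive test after sustained LFS. Patients with different LFS durations could be pooled in the group t-test on the UPDRS (section 14) and in the BDI and NPI ANOVAs over time (section 15).

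The call is the only BDI/NPI check between E1 and E2, and a BDI of 20 or more ends the study for that patient (section 14). If LFS runs from E1 and the call is timed from E2, the check comes later in the exposure than sections 11 and 14 intend.

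**Working it through.** **Inputs.** Gap g from E1 to E2: 3, 4 or 5 days (section 12), or 3 or 4 days (section 10). E1 on day 22, 23 or 24 (section 12). Target exposure 48 h (section 12). Call 24 h before E2 (section 10).

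**The plan's own figure.** Switch-on two days before E2 gives 2 × 24 = 48 h of LFS at E2. The call, 24 h before E2, falls at 48 − 24 = 24 h of LFS. Both match the plan. The switch-on falls 24g − 48 h after E1.

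**LFS on from the end of E1 until E2.** Exposure = 24g h; ratio to target = 24g/48; LFS hours at the call = 24g − 24, which is 24g − 48 h later in the exposure than the stated 24 h.

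| Gap g (days) | LFS at E2 if on from E1 | Ratio to 48 h | LFS hours at call | Delay of call | Switch-on after E1 if started two days before E2 | E2 day after lead surgery |
|---|---|---|---|---|---|---|
| 3 | 72 h | 1.5 | 48 h | 24 h | 24 h | 25-27 |
| 4 | 96 h | 2.0 | 72 h | 48 h | 48 h | 26-28 |
| 5 (section 12 only) | 120 h | 2.5 | 96 h | 72 h | 72 h | 27-29 |

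**LFS on at the end of E1 and off after exactly 48 h.** Stimulation would then be off for 24g − 48 = 24, 48 or 72 h before E2. That contradicts continuous stimulation up to and during E2.

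**The gap that reconciles the start times.** Setting 24g = 48 gives g = 2. E2 would fall on days 24-26, outside both stated gaps.

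**Visit count.** Baseline, E1 and E2 use up the 3 on-site sessions in section 10, and the one call is the safety call. A switch-on 24-72 h after E1 (24-48 h with the section 10 gap) is not among them. That it is a clinic contact is an inference: patients go home after it, section 23 places all research procedures at UC Davis, and section 24 lists generator reprogramming as an investigator task. No remote switch-on is described.

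**Calendar.** The nine combinations of E1 day (22, 23, 24) and gap (3, 4, 5) put E2 on days 25, 26, 27, 26, 27, 28, 27, 28 and 29. One of the nine, day 29, lies outside the fourth week and past the usual 4-week treatment start. A 3-4 day gap keeps E2 on days 25-28.

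**The case against.** The strongest reply is that 48 h is the one point on which all the texts agree, and that 72-120 h arises only by joining the caption's start to a gap the caption does not state. This stands in part: the target is consistent, and the caption read alone implies a return at 48 h. It does not remove the problem, because the section 12 text itself allows LFS to be left on after E1 and sets E2 3-5 days later.

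Other points that stand in part:

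- **The late call is conditional.** A site that times the call from the start of LFS, as sections 11 and 14 do, calls at 24 h whatever the start. The delay occurs only if section 10's timing is followed with LFS on from E1.
- **The uncounted contact is partly inferred.** Section 10 totals experimental sessions, and a programming contact without testing might not be one. But the same section also numbers the on-site visits, with E1 and E2 as the second and third, which leaves no place between them for another.
- **Day 29 is already excluded** by section 10's fourth-week limit, and the treatment start is only typical. One of nine combinations is a count, not a probability.
- **No effect on results is shown.** Nothing in the documents indicates that outcomes differ between 48 h and 72-120 h of LFS, and the study is not powered for efficacy.
- **The Figure 2 drawing was not available**, so the point rests on its caption.

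**Conclusion.** The concern holds. The rule for delivering sustained LFS contradicts itself, and nothing in the document says which start applies. LFS left on from E1 lasts 72-120 h at E2 with the section 12 gap, or 72-96 h with the section 10 gap, against 48 h intended. If the call is also timed by section 10, it comes 24-72 h later in the exposure than stated. A start two days before E2 reproduces the 48 h and the 24 h call, but relies on a contact that section 10 does not list.

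These figures assume whole-day gaps and uninterrupted LFS until E2. The measures at E2 still follow sustained LFS, and the comparison of low, high and no stimulation within E1 is not affected. The size of any effect on UPDRS, BDI, NPI or cognitive results cannot be estimated from the documents.

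**What to change.** Adopt one schedule throughout.

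1. **LFS on at the end of E1, E2 48 h later (days 24-26).** Change the gap to 2 days in sections 10 and 12. Delete the option of switching off after E1. Replace the switch-on two days before E2 with patients going home from E1 with LFS running. The visit count stays as it is, and the call falls at 24 h by both definitions.
2. **LFS on two days before E2.** Set the gap to 3-4 days in both sections, with E2 no later than day 28 and before the patient's treatment switch-on. Delete the option of leaving LFS on after E1. Change the Figure 2 caption to show stimulation off after E1 and LFS on 48 h before E2. Add the switch-on contact to section 10.

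Under either option, record the actual times of switch-on, call and E2, and report LFS hours with the E2 results.

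The cost is wording in sections 10 and 12 and the caption, plus three recorded times per patient. Option 1 makes visit scheduling tighter. Option 2 makes explicit one extra programming contact per patient, probably on site; the session and time lists in section 12, the compensation and travel terms in section 9 and the consent forms should be checked against it. The Figure 2 drawing should be checked against whichever schedule is chosen.
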